1.9. Trial Objectives

1.9.1. Primary Objective

Part A (Phase 1; dose escalation):

- To determine the safety and tolerability of IV administration of CTL-002 as monotherapy and in combination with an anti-PD-1 checkpoint inhibitor in subjects with advanced-stage solid tumors that relapsed post or were refractory to a prior anti-PD-1/PD-L1 therapy.

Part B (Phase 2a; expansion):

- To explore the preliminary anti-tumor activity of CTL-002 administered in combination with an anti-PD-1 checkpoint inhibitor in subjects with advanced-stage, relapsed/refractory solid tumors in non-curable state as per current clinical knowledge that have either:
 - (1) bladder cancer, hepatocellular cancer, non-small cell lung cancer, cutaneous squamous-cell carcinoma or melanoma (for melanoma, only cutaneous and mucosal forms, not uveal/ocular) (approved anti-PD-1/PD-L1 indications) that relapsed on or were primary refractory to prior anti-PD-1/PD-L1 therapy with an approved anti-PD-1/PD-L1 compound, or
 - (2) colorectal cancer (micro-satellite stable [MSS]/mismatch-repair competent) and have not received any prior anti-PD-1/PD-L1 therapy, or
 - (3) biomarker cohort with mixed solid tumors (“basket” cohort) that are relapsed on or were primary refractory to prior anti-PD-1/PD-L1 therapy with an approved anti-PD-1/PD-L1 compound.
- To confirm the safety and tolerability of CTL-002 administered as an IV infusion, in combination with an anti-PD-1 checkpoint inhibitor

1.9.2. Secondary Objectives

Part A (Phase 1; dose escalation):

- To explore the PK of CTL-002 administered as monotherapy and in combination with an anti-PD-1 checkpoint inhibitor
- To explore the pharmacodynamics of CTL-002 administered as monotherapy and in combination with an anti-PD-1 checkpoint inhibitor

- To determine the recommended dose(s) for the expansion cohorts (Part B [expansion]) of CTL-002 administered as monotherapy and in combination with an anti-PD-1 checkpoint inhibitor
- To explore the preliminary anti-tumor activity of CTL-002 administered in combination with an anti-PD-1 checkpoint inhibitor
- To explore the effect of CTL-002 on prevention of anorexia and muscle wasting (cachexia)

Part B (Phase 2a; expansion):

- To confirm and further explore the PK/pharmacodynamics of CTL-002 given in combination with an anti-PD-1 checkpoint inhibitor
- To confirm the recommended Phase 2 dose (RP2D) of CTL-002

1.9.3. Exploratory Objectives

Part A (Phase 1; dose escalation):

- To explore additional pharmacodynamics in peripheral blood and tumor tissue (e.g., GDF-15 levels, immune cell phenotypes and activation status), with CTL-002 administered as monotherapy and in combination with an anti-PD-1 checkpoint inhibitor

Part B (Phase 2a; expansion):

- To assess the antitumoral activity of CTL-002 in combination with cemiplimab (checkpoint inhibitor) using World Health Organization (WHO) bidimensional measurements in subjects with advanced-stage cutaneous squamous-cell carcinoma that relapsed on or were primary refractory to a prior anti-PD-1/PD-L1 therapy
- To explore the preliminary anti-tumor activity of CTL-002 administered in combination with an anti-PD-1 checkpoint inhibitor in patients with stable disease after receiving stereotactic radiotherapy
- To explore additional pharmacodynamics in peripheral blood and tumor tissue (e.g., GDF-15 level, immune cell phenotypes, and activation status), with CTL-002 administered in combination with an anti-PD-1 checkpoint inhibitor in patients with stable disease after receiving stereotactic radiotherapy.

1.10. Trial Endpoints

1.10.1. Primary Endpoints

Part A (Phase 1; dose escalation):

- Evaluation of the number of subjects with AEs, including serious adverse events (SAEs), clinical laboratory data, vital signs, electrocardiograms (ECGs), physical examination (including neurological assessment) and Eastern Cooperative Oncology Group (ECOG) performance status

Determination of DLTs and maximum tolerated dose (MTD) in Part A of the study using the National Cancer Institute Common Terminology Criteria for Adverse Events (NCI-CTCAE) Version 5.0

Part B (Phase 2a; expansion):

- Evaluation of the clinical efficacy according to Response Evaluation Criteria in Solid Tumors (RECIST) V1.1 of CTL-002 in combination with an anti-PD-1 checkpoint inhibitor by assessment of:
 - The proportion of subjects with tumor shrinkage, a confirmed partial response (PR) and/or complete response (CR), and overall response rate (ORR)
 - The interval between the date of first CTL-002 administration and first documented evidence of a PR or CR (time to response [TTR])
 - The interval between the date of first documented evidence of PR or CR, until first documented evidence of disease progression or death, due to any cause (duration of response [DOR])
 - The interval between the date of first CTL-002 administration and the earliest date of disease progression or death (progression free survival [PFS])
 - The interval between the date of first CTL-002 administration and date of death due to any cause (overall survival [OS])
- Evaluation of the number of subjects with AEs, including SAEs, clinical laboratory data, vital signs, ECGs, physical examination (including neurological assessment), and ECOG performance status

1.10.2. Secondary Endpoints

Part A (Phase 1; dose escalation):

- Evaluation of PK parameters of CTL-002 (e.g., C_{max} , AUC, and $t_{1/2}$)
- Evaluation of treatment-emergent cytokine and chemokine profiles in peripheral blood
- Evaluation of treatment-induced anti-drug antibodies (ADA)
- Evaluation of the clinical efficacy according to RECIST V1.1 of CTL-002 as monotherapy and in combination with an anti-PD-1 checkpoint inhibitor by assessment of:
 - The proportion of subjects with tumor shrinkage, a confirmed PR and/or CR, and ORR
 - The interval between the date of first CTL-002 administration and first documented evidence of a PR or CR (TTR)
 - The interval between the date of first documented evidence of PR or CR, until first documented evidence of disease progression or death, due to any cause (DOR)
 - The interval between the date of first CTL-002 administration and the earliest date of disease progression or death (PFS)
 - The interval between the date of first CTL-002 administration and date of death due to any cause (OS)
- To assess appetite, body mass index (BMI), and muscle mass (e.g., L3 skeletal muscle index [L3SMI])

Part B (Phase 2a; expansion):

- Evaluation of PK parameters of CTL-002 (e.g., maximum concentration [C_{max}], area under the curve [AUC], and half-life [$t_{1/2}$])
- Evaluation of treatment-emergent cytokine and chemokine profiles in peripheral blood
- Evaluation of treatment-induced ADA
- Evaluation of GDF-15 serum levels and their correlation with pharmacodynamics and clinical response

1.10.3. Exploratory Endpoints**Part A (Phase 1; dose escalation):**

- Evaluation of GDF-15 serum levels and their correlation with pharmacodynamic and clinical response
- Immune cell phenotyping including activation status and immune cell infiltration pattern in tumor tissue
- Molecular profiling (e.g., transcriptional profiling, mutational status, mutational burden of tumor tissue)
- To assess anti-tumor efficacy (PR, CR, DOR, PFS, and OS) of CTL-002 in combination with an anti-PD-1 checkpoint inhibitor using iRECIST ([Seymour et al., 2017](#)), criteria in solid tumors in subjects with advanced-stage solid tumors that relapsed post or were refractory to a prior anti-PD-1/PD-L1 therapy

Part B (Phase 2a; expansion):

- In subjects that undergo tumor biopsy: Immune cell phenotyping including activation status and immune cell infiltration pattern in tumor tissue
- In subjects that undergo tumor biopsy: Molecular profiling (e.g., transcriptional profiling, sequencing of genes of interest, mutational status, mutational burden of tumor tissue) and evaluation of GDF-15 levels
- To assess anti-tumor efficacy (PR, CR, DOR, PFS, and OS) of CTL-002 in combination with an anti-PD-1 checkpoint inhibitor using iRECIST criteria ([Seymour et al., 2017](#)), in solid tumors that relapsed on or were primary refractory to a prior anti-PD-1/PD-L1 therapy
- To assess in subjects with advanced-stage cutaneous squamous-cell carcinoma that relapsed on or were primary refractory to a prior anti-PD-1/PD-L1 therapy: the anti-tumor efficacy (PR, CR, DOR, PFS, and OS) of CTL-002 in combination with cemiplimab checkpoint inhibitor using WHO bidimensional measurements
- The proportion of subjects with tumor shrinkage, a confirmed partial PR and/or CR, and ORR after receiving stereotactic radiotherapy according to RECIST V1.1 (ORR-2)
- The interval between application of stereotactic radiotherapy and first documented evidence of a PR or CR according to RECIST V1.1 (TTR-2)
- The interval between the date of first documented evidence of PR or CR after having received stereotactic radiotherapy, until first documented evidence of disease progression or death, due to any cause according to RECIST V1.1 (DOR-2)

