2.3. Optional Stereotactic Radiotherapy

All subjects in the phase 2 part that achieve/maintain stable disease by week 24 but do not show tumor shrinkage beyond -10% as per RECIST criteria can undergo if desired by the treating physician and agreed by the patient stereotactic radiotherapy of one or more tumor lesions to increase neoantigen exposure and potential for response improvement (as was seen in two phase 1 patients). This should always be pre-discussed with the medical representative of the sponsor and the radiotherapy area should not include all lesions that are used for RECIST response assessment to allow for abscopal antitumor effect assessment.

Radiotherapy should be performed according to local hospital's regulations.

Note: In case of initiation of stereotactic radiotherapy in addition to study treatment, an optional tumor biopsy should be performed no earlier than 4 weeks after initiation of radiotherapy, if seen as safe and medically feasible by the treating physician.

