12. APPENDICES

APPENDIX 1: RESPONSE EVALUATION CRITERIA IN SOLID TUMORS (RECIST) VERSION 1.1

The following paragraphs represent a reference to the RECIST criteria (Version 1.1). The complete criteria are available at <https://recist.eortc.org/recist-1-1-2/> and are included in the published RECIST document.

At baseline, tumor lesions/lymph nodes will be categorized as measurable or non-measurable.

For Part B, only subjects with obvious measurable disease at baseline should be included in the present clinical trial.

A 1.1 Measurability of Tumor Lesions at Baseline – Definitions

Measurable disease – the presence of at least one measurable lesion. If the measurable disease is restricted to a solitary lesion, its neoplastic nature should be confirmed by cytology/histology.

Measurable lesions – *tumor lesions* that can be accurately measured in at least one dimension (longest diameter to be recorded) as ≥ 20 mm with chest x-ray, and as ≥ 10 mm with CT scan or clinical examination (using calipers). Bone lesions are considered measurable only if assessed by CT scan and have an identifiable soft tissue component that meets these requirements (soft tissue component ≥ 10 mm by CT scan). *Malignant lymph nodes* must be ≥ 15 mm in the short axis to be considered measurable; only the short axis will be measured and followed. All tumor measurements must be recorded in millimeters (or decimal fractions of centimeters) by use of a ruler or calipers. Tumor lesions situated in a previously irradiated area, or in an area subjected to other loco-regional therapy, are usually not considered measurable unless there has been demonstrated progression in the lesion.

Non-measurable lesions – all other lesions (or sites of disease), including small lesions are considered non-measurable disease. Bone lesions without a measurable soft tissue component, leptomeningeal disease, ascites, pleural/pericardial effusions, lymphangitis cutis/pulmonis, inflammatory breast disease, lymphangitic involvement of lung or skin and abdominal masses followed by clinical examination are all non-measurable. Nodes that have a short axis < 10 mm at baseline are considered non-pathological and should not be recorded or followed.

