Target lesions – when more than one measurable tumor lesion or malignant lymph node is present at baseline all lesions up to *a maximum of 5 lesions total* (and a maximum of *2 lesions per organ*) representative of all involved organs should be identified as target lesions and will be recorded and measured at baseline. Target lesions should be selected on the basis of their size (lesions with the longest diameter), be representative of all involved organs, but in addition should be those that lend themselves to *reproducible repeated measurements*.

Note: Pathological nodes must meet the criterion of a short axis of ≥ 15 mm by CT scan and only the short axis of these nodes will contribute to the baseline sum.

At baseline, the sum of the target lesions (longest diameter of tumor lesions plus short axis of lymph nodes: overall maximum of 5) is to be calculated and recorded.

Non-target lesions – all non-measurable lesions (or sites of disease) including pathological nodes (those with short axis ≥ 10 mm but < 15 mm), plus any measurable lesions over and above those listed as target lesions are considered *non-target lesions*. Measurements are not required but these lesions should be noted at baseline and should be followed as “present” or “absent”.

All baseline evaluations should be performed as closely as possible to the beginning of treatment and never more than 4 weeks before the beginning of the treatment.

A 1.2 Methods of Measurements

The same method of assessment and the same technique should be used to characterize each identified and reported lesion at baseline and during follow-up.

Assessments should be identified on a calendar schedule and should not be affected by delays in therapy, which may be treatment arm dependent. While on study, all target lesions recorded at baseline should have their actual measurements recorded on the eCRF at each subsequent evaluation, even when very small (e.g., 2 mm). If it is the opinion of the radiologist that the lesion has likely disappeared, the measurement should be recorded as 0 mm. If the lesion is believed to be present and is faintly seen but too small to measure, a default value of 5 mm should be assigned. For lesions which fragment/split add together the longest diameters of the fragmented portions; for lesions which coalesce, measure the maximal longest diameter for the “merged lesion”.

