where known residual benign tumors can remain). When effusions are known to be a potential adverse effect of treatment (e.g., with certain taxane compounds or angiogenesis inhibitors), the cytological confirmation of the neoplastic origin of any effusion that appears or worsens during treatment when the measurable tumor has met criteria for response or SD is advised to differentiate between response or SD and PD.

A 1.3 Tumor Response Evaluation

All subjects will have their BEST RESPONSE from the start of study treatment until the end of treatment classified as outlined below. Refer to [Table 11](#) and [Table 12](#).

Complete Response (CR) – disappearance of all *target* and *non-target* lesions and normalization of tumor markers. Pathological lymph nodes must have short axis measures <10 mm (*Note: continue to record the measurement even if <10 mm and considered CR*). Tumor markers must have normalized. Residual lesions (other than nodes <10 mm) thought to be non-malignant should be further investigated (by cytology or PET scans) before CR can be accepted.

Partial Response (PR) – at least a 30% decrease in the sum of measures (longest diameter for tumor lesions and short axis measure for nodes) of target lesions, taking as reference the baseline sum of diameters. Non-target lesions must be non-PD.

Stable Disease (SD) – neither sufficient shrinkage to qualify for PR nor sufficient increase to qualify for PD taking as reference the smallest sum of diameters on study.

Progressive Disease (PD) – at least a 20% increase in the sum of diameters of measured lesions taking as references the smallest sum of diameters recorded on study (including baseline) AND an absolute increase of ≥ 5 mm. Appearance of new lesions will also constitute PD (including lesions in previously unassessed areas). In exceptional circumstances, unequivocal progression of non-target disease may be accepted as evidence of disease progression, where the overall tumor burden has increased sufficiently to merit discontinuation of treatment, for example where the tumor burden appears to have increased by at least 73% in volume (which is the increase in volume when all dimensions of a single lesion increase by 20%). Modest increases in the size of one or more non-target lesions are NOT considered unequivocal progression. If the evidence of PD is equivocal (target or non-target), treatment may continue until the next assessment, but on further documentation, the earlier date must be used.

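### ORR-2, TTR-2 and DOR-2 count irradiated target lesions, so they cannot by themselves separate a local radiotherapy effect from an abscopal or systemic one

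*Protocol*

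**What the plan says.** Section 1.10.3 (Part B), repeated in the synopsis, lists three endpoints for subjects given stereotactic radiotherapy on study:

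- ORR-2: "The proportion of subjects with tumor shrinkage, a confirmed partial PR and/or CR, and ORR after receiving stereotactic radiotherapy according to RECIST V1.1 (ORR-2").
- TTR-2: "The interval between application of stereotactic radiotherapy and first documented evidence of a PR or CR according to RECIST V1.1 (TTR-2").
- DOR-2, which begins at the first such response and ends at progression or death: "The interval between the date of first documented evidence of PR or CR after having received stereotactic radiotherapy, until first documented evidence of disease".

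None of them names a lesion set or a reference scan, so RECIST V1.1 as set out in Appendix 1 applies. A 1.2 states that "all target lesions recorded at baseline should have their actual measurements recorded on the eCRF at each subsequent evaluation". A 1.3 defines PR as "at least a 30% decrease in the sum of measures (longest diameter for tumor lesions and short axis measure for nodes) of target lesions", with the baseline sum as reference.

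Section 2.3 offers radiotherapy of one or more lesions to subjects with stable disease by week 24 whose shrinkage has not gone beyond -10%. It adds that "the radiotherapy area should not include all lesions that are used for RECIST response assessment to allow for abscopal antitumor effect assessment".

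The matching objective in section 1.9.3 is anti-tumor activity of CTL-002 with anti-PD-1 in these subjects. Section 1.3 describes the abscopal effect as shrinkage in lesions that were not irradiated.

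**The concern.** The field rule in section 2.3 preserves untreated disease to observe, but the endpoints do not use it. They add the irradiated and non-irradiated target lesions into one sum, and a fall in that sum may come from either. A PR can then be credited when radiotherapy shrank the treated lesion and nothing happened elsewhere. Such a PR answers neither the abscopal question nor the objective in section 1.9.3, because shrinkage of a directly irradiated lesion cannot be attributed to the drug combination.

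The protocol is careful about this in other places. Inclusion criterion 8 asks for a measurable lesion that has not been irradiated. Section 6.2.5.1 keeps biopsied lesions out of the RECIST assessment. A 1.1 says: "Tumor lesions situated in a previously irradiated area, or in an area subjected to other loco-regional therapy, are usually not considered measurable", with an exception for lesions that have since progressed. But A 1.1 concerns measurability at baseline, and no text extends it to a target lesion irradiated during the study.

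What is at stake is a misattributed signal. Section 1.8.5 suggests that experience with radiotherapy may guide further development of the combination.

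**Working it through.** The protocol gives no sample size, rate or power for these endpoints, so there is no stated figure to reproduce. The check is RECIST arithmetic from the protocol's own rules.

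**Inputs from the protocol**
- PR: target sum at or below 70% of the baseline sum (A 1.3).
- Up to 5 target lesions (A 1.1).
- Change from baseline before radiotherapy, d: from -10% (section 2.3) to just under +20%, the PD limit when baseline is the smallest sum (A 1.3).
- One or more lesions irradiated, but not all RECIST lesions (section 2.3).

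**Assumptions**
- k target lesions of equal size, m of them irradiated (m < k).
- The other lesions stay exactly at their pre-radiotherapy size.

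**Formula.** Set the baseline sum to 100. Before radiotherapy the sum is 100(1+d), and the irradiated part is 100(1+d)·m/k. The local shrinkage needed for a PR is

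s = [100(1+d) − 70] / [100(1+d)·m/k].

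If s exceeds 100%, a local-only PR is impossible.

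**Examples**
- 1 of 2, d = -10%: (90 − 70)/45 = 44%.
- 1 of 2, d = 0: (100 − 70)/50 = 60%.
- 1 of 2, d = +19%: (119 − 70)/59.5 = 82%.
- 4 of 5, d = -10%: (90 − 70)/72 = 28%.
- 1 of 5, d = -10%: (90 − 70)/18 = 111%, impossible. Complete disappearance leaves a sum of 72, or -28%.

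| Irradiated | d = -10% | d = 0 | d = +10% | d = +19% |
|---|---|---|---|---|
| 1 of 2 | 44% | 60% | 73% | 82% |
| 1 of 3 | 67% | 90% | impossible | impossible |
| 2 of 3 | 33% | 45% | 55% | 62% |
| 1 of 4 | 89% | impossible | impossible | impossible |
| 2 of 5 | 56% | 75% | 91% | impossible |
| 4 of 5 | 28% | 38% | 45% | 51% |
| 1 of 5 | impossible | impossible | impossible | impossible |

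**General limit.** Even if the irradiated lesions disappear, they must make up at least 1 − 0.70/(1+d) of the pre-radiotherapy sum. That is 22% at d = -10%, 30% at d = 0 and 41% at d = +19%.

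**Growth elsewhere.** Take two target lesions of 50 each. If the irradiated one falls to 10 and the other grows to 60, the sum is 70. That is a PR on the target sum although the untreated lesion grew by 20%.

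**CR.** A 1.3 requires every target and non-target lesion to disappear, so a CR cannot be purely local while a non-irradiated lesion persists.

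**Under the repair.** Sum only the non-irradiated target lesions against their own study baseline. If they do not change after radiotherapy, their change stays at d, between -10% and +19%, and never reaches -30%. This assumes that the earlier change was shared equally across lesions.

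**The case against.** The strongest reply is that the endpoints do what the objective says. Section 1.9.3 asks about anti-tumor activity after radiotherapy without using the word abscopal, and section 2.3 speaks of improving response. That is a fair reading of the objective. It does not remove the problem, because the objective is about the drug combination and section 2.3 gives abscopal assessment as the reason for its field rule.

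A second reply is that this belongs in the SAP. Lesions are followed under unique numbers (section 6.2.5.1) and target lesions are measured individually (A 1.2), so an analysis of untreated lesions could be derived. This stands in part. But the protocol positively fixes RECIST V1.1 as the criterion, and nothing requires recording which numbered lesions were irradiated.

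Several stronger readings are tempting, and the documents do not support them:

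- **The endpoints cannot show an abscopal effect at all, or mostly measure local effect.** They can show one for a CR, where the irradiated lesion is non-target, and where it is a small share of the sum, such as one of five equal lesions. The protocol does not say how many lesions or what share of tumor burden will be irradiated.
- **A definite fraction of ORR-2 responses would be local only.** Any such rate depends on an assumed distribution of local shrinkage. For one of two lesions at d = 0 (threshold 60%), shrinkage spread evenly over 30–100% gives (100 − 60)/70 = 57%; spread over 0–100% it gives 40%. The protocol supports neither choice, and section 1.3 describes the intended radiotherapy as non-ablative.
- **Almost any local shrinkage counts as tumor shrinkage.** This fails above baseline. At d = +10%, the sum returns to baseline only after 10/55 = 18% local shrinkage with one of two irradiated, and 10/22 = 45% with one of five.
- **The study-baseline reference is itself an error.** A subject at -10% needs a further 1 − 70/90 = 22% fall and one at +10% needs 1 − 70/110 = 36%, but that is how RECIST works. Resetting the reference is a preference.

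**Conclusion.** The concern holds in limited form. Under the stated rules, shrinkage of irradiated target lesions alone can produce a PR in many configurations, so ORR-2 and TTR-2 mix local and systemic effects and DOR-2 inherits the same responders. The field restriction does not cure this.

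The size depends on the share of the target sum irradiated and on the change before radiotherapy. With equal lesions and the others unchanged, the local shrinkage needed runs from 28% (four of five at -10%) to a level that cannot be reached (one of five at any eligible value). Unequal lesions would move these thresholds, and the general limit of 22% to 41% of the sum then applies.

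The importance is modest. These are three exploratory endpoints in an optional subgroup, section 8.1 plans no formal comparisons, and no decision rule is attached to them. The point does not extend to the primary endpoints.

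**What to change.** In section 1.10.3 and the synopsis, define ORR-2, TTR-2 and DOR-2 on the non-irradiated lesions, with new lesions and unequivocal non-target progression still counting as PD. Flag the irradiated lesion numbers in the eCRF. Report the full-sum RECIST V1.1 result and the local response of the irradiated lesions separately.

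State the reference scan. Keeping the study baseline already prevents local-only PRs under the equal-lesion assumption. The last scan before radiotherapy may be added as a supplementary reference; it would help where lesions had changed unequally beforehand.

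The cost is protocol and SAP wording and one eCRF flag per irradiated lesion. Target lesions are already numbered and measured individually, and scans are already scheduled every 8 weeks (6–9 weeks in the cutaneous squamous-cell cohort), so no extra imaging is needed. Nothing changes in who receives radiotherapy or how. The downside is a sum over fewer lesions, which is slightly noisier, and a lower ORR-2.
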